9.7.1.1. Analysis Populations

9.7.1.1.1. Populations

The Full Analysis Set will include all patients who received at least one dose of investigational product as indicated on the dosing record. Patients will be analyzed in the group according to the treatment received. All efficacy and safety variables will be analyzed using the Full Analysis Set and only observed data will be included.

9.7.1.1.2. Analysis Eyes

Patients in the FAS will have at least one eye that qualifies based on the criteria in the protocol. Both eyes may qualify based on the criteria.

Efficacy analyses will be performed for the study eye; safety analyses will be presented for both eyes, by study eye and non-study eye.

The study eye is defined as the eye meeting all inclusion criteria and no exclusion criteria, and with the worse BCVA assessed at screening and confirmed at the Baseline (Day 1) visit. If both eyes meet all of the inclusion/exclusion criteria and BCVA values are identical for both eyes, the patient may choose the eye for study enrollment, or else the right eye will be selected as the study eye.

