- h. IOP measurement will be performed prior to and after AG-73305 injection at Baseline/Day1. After injection, IOP will be measured within 15 minutes using a tono-pen or tono-pen like device. If IOP >30mmHg, repeat IOP measurement at 15±5 minutes post injection until pressure is reduced
- i. Color fundus photos, OCT-A and SD-OCT images will be submitted to a reading center for grading; not required for eligibility
- j. OCT-A is to be performed at baseline and at the visit (OU) when **Rescue** treatment is given. OCT-A is to be performed prior to the rescue treatment
- k. Dilated fundus exam
- l. Prednisolone acetate 1% ophthalmic suspension will be provided to patients, who will be instructed to prophylactically treat the study eye QID 2 days prior to the Baseline visit. Patients will be instructed to taper based on the Day 2 follow-up visit
- m. Within 15 minutes following intravitreal injection, a post-injection assessment will be done, including checking for count fingers or hand motion vision
- n. At selected sites, blood (~10 mL) will be collected for plasma drug monitoring on Day 1 pre-dose (all Cohorts), 1 hour (Cohort 1 and 2 only), 3 hours (all Cohorts), 8 hours (all Cohorts) and 24 hours post dose (Cohort 3 and 4 only), Week 1 (all Cohorts), and Week 4 (all Cohorts) in approximately 2-4 patients.
- o. ~20 mL of blood will be collected on Day 1 pre-dose and Weeks 1, 4, 8 and 24 from all patients for anti-drug antibody assessments.

Additional examinations and unscheduled visits can be included as safety concerns arise.

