9.7.1. Statistical and Analytical Plans

General Conventions

Summary statistics for the data collected during this study will be presented to give a general description of the patients studied. Data from all sites will be combined in the computation of these descriptive summaries. Categorical variables will be summarized by the frequency and percentage of patients in each category. Continuous variables will be summarized using N, mean, standard deviation (SD), median, minimum, and maximum values.

Number of patients, minimums, and maximums will be calculated to the same number of decimal places as the source data. Means, medians, standard deviations, and quartiles will be calculated to one more decimal place than the source data. Percentages will be calculated to the nearest one decimal place. Zero count cells will be displayed as “0” with percentage of (0%). Unless otherwise noted, summaries will be performed by the treatment group and presented in the order of: AG-73305, 0.5 mg; AG-73305, 1 mg; AG-73305, 2 mg; AG-73305, 4 mg.

Baseline values will be defined as the last measurement prior to dosing of study medication. Ocular measurements will use the most recent measurement for each eye.

Numeric laboratory, pharmacokinetic, and immunogenicity data may be recorded at limits of detection (with a ‘<’ or ‘>’ sign, e.g., < 0.1 or > 0.1). To summarize laboratory data, the original value will be converted to one unit less or more at the level of measured precision (e.g. 0.4 in the case of < 0.5 and to 0.6 in the case of > 0.5). For pharmacokinetic data, for Time = 0 (predose), any result that is below the level of quantitation (BLQ) is set to zero; all other timepoints are set to missing for any computations. For immunogenicity, any titer < Value (a negative result) is set to zero. Summary tables for immunogenicity titer will not include these negative results.

The actual values will be presented in the data listings.

All data collected in this study will be presented in individual patient data listings for all patients.

Computations for all results will be performed using SAS (Version 9.4, SAS/STAT 15.2) computer software package (SAS Institute, Inc, 2013, 2020), unless otherwise specified.

Strata and Covariates

Not applicable.

Subgroups

Not applicable.

Multiplicity

Not applicable.

Missing Data and Outliers

Every attempt will be made to capture all study data. All analyses will utilize observed data only.

Visit Windows

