9.7.1.5.1. Primary Efficacy Analysis

The key efficacy measure is best-corrected visual acuity score of the study eye using the ETDRS as assessed by certified Investigator or designee. The endpoint is the change from baseline in ETDRS letters at Week 4, so scores from Day 1 and Week 4 will be analyzed. Final scores will be calculated as Week 4 minus Day 1 BCVA letter counts. A positive result will indicate more letters gained following AG-73305 injection, while a negative score indicates worsening of vision. Observed and change from baseline in BCVA letter count at other visits will be summarized in a similar fashion to the key efficacy measure.

In addition, change from baseline in BCVA letter count as measured by ETDRS at each visit and the proportion of study eyes with ≥ 5 , ≥ 10 , and ≥ 15 BCVA letter increase from baseline will be analyzed.

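### The Day 1 acuity reading both confirms the worse eye and serves as efficacy baseline; depending on what a failed confirmation means, this biases the Week 4 BCVA change modestly upward in patients with two qualifying eyes

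*SAP*

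**What the plan says.** SAP 9.7.1.1.2 allows the two eyes to compete ("Both eyes may qualify based on the criteria") and defines the study eye as the qualifying eye "with the worse BCVA assessed at screening and confirmed at the Baseline (Day 1) visit". Its only tie rule covers identical acuity in both eyes.

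SAP 9.7.1 sets the baseline: "Baseline values will be defined as the last measurement prior to dosing of study medication". SAP 9.7.1.5.1 applies this to the primary endpoint: "Final scores will be calculated as Week 4 minus Day 1 BCVA letter counts". The responder proportions (at least 5, 10 and 15 letters gained) use the same baseline.

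Protocol 1.3, footnote l, covers prednisolone, which is dispensed at Screening to patients "who will be instructed to prophylactically treat the study eye QID 2 days prior to the Baseline visit". SAP Appendix I repeats the footnote. The screening window closes on Day -2, and the inclusion/exclusion review is marked at Screening only.

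There is no randomization. SAP 9.7.2 gives 3-8 patients per cohort without a power calculation.

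**The concern.** One noisy reading does two jobs. If a patient stays in the analysis with a given eye only when that eye reads lower than its fellow on Day 1, retained eyes will on average have been measured too low that day. The Week 4 reading carries no such condition. The difference between the two then tends upward even if nothing has changed in the eye.

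There is no comparator to cancel this, so it would remain in each cohort's mean change and responder proportions. It would favour the stated hypothesis that at least one dose shows benefit, which is judged partly on BCVA.

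There is also a problem of order. The eye must be named and pre-treated about two days before the visit that completes its definition. If the ranking reverses on Day 1, the pre-treated eye and the eye that fits the definition differ.

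**Working it through.** **Figures in the plan.** The documents give no BCVA effect size, SD or power to reproduce. The only computed design figures, in SAP Table 2, follow 1 - (1 - p)^n (for example 1 - 0.95^3 = 0.143). All 24 cells agree to rounding, but they do not bear on this point.

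**Assumed inputs (none is in the documents).**
- σ: SD of one acuity reading, 4 letters (range 3-5).
- τ: SD of the true difference between the two eyes, 8 letters.
- ρ: correlation of the two eyes' errors within a visit, 0 or 0.5.
- Normal errors, independent between visits, and no true change in acuity.

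**Formulas**, for patients with two qualifying eyes:
- S = √(2σ²(1 - ρ) + τ²), the SD of the observed between-eye difference at one visit.
- c = σ²(1 - ρ) / S.
- f = arccos(τ² / S²) / π, the probability that the worse eye differs between Screening and Day 1.
- Reversal excludes the patient: expected gain = c / (√(2π) × (1 - f)).
- Reversal switches the eye: expected gain = c × √(2/π).
- Screening eye always kept: expected gain = 0, because the Day 1 error played no part in the choice.

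**Central case, σ = 4, τ = 8, ρ = 0.** S = √(32 + 64) = 9.80. c = 16 / 9.80 = 1.633. f = arccos(64/96) / π = 0.268.
- Exclusion: 1.633 / (2.507 × 0.732) = 0.89 letters.
- Switching: 1.633 × 0.798 = 1.30 letters.

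**Same case, ρ = 0.5.** S = √(16 + 64) = 8.94. c = 8 / 8.94 = 0.894. f = arccos(64/80) / π = 0.205.
- Exclusion: 0.894 / (2.507 × 0.795) = 0.45 letters.
- Switching: 0.894 × 0.798 = 0.71 letters.

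**Truly equal eyes, σ = 4, ρ = 0.** c = 16 / √32 = 2.828, f = 0.5, and both rules give 2.26 letters.

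Simulation agrees with these results. Over the range of σ with τ = 8:

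| Reading SD | Exclude, ρ = 0 | Switch, ρ = 0 | Exclude, ρ = 0.5 | Switch, ρ = 0.5 | Keep Screening eye |
|---|---|---|---|---|---|
| 3 | 0.51 | 0.79 | 0.26 | 0.42 | 0.0 |
| 4 | 0.89 | 1.30 | 0.45 | 0.71 | 0.0 |
| 5 | 1.35 | 1.87 | 0.70 | 1.06 | 0.0 |

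Over a wider grid (σ 2-5, τ 3-18, ρ = 0, exclusion) the gain runs from 0.1 to 2.4 letters. For fixed true differences with σ = 4, ρ = 0 and exclusion, it is 1.1 letters for eyes 5 letters apart and about 0.25 for eyes 10 apart.

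**Responders**, by simulation in the central case under exclusion: at least 5 letters, 22.7% against 18.8% if the Screening eye is kept; at least 10 letters, 4.9% against 3.8%.

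**Scale.** If half of a cohort had two qualifying eyes (an illustration; the share is not given), the cohort mean would shift by 0.5 × 0.89 = 0.45 letters. With an assumed SD of change of 8 letters, the standard error of a 6-patient mean is 8 / √6 = 3.3 letters.

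**The case against.** The strongest reply is that the bias needs a rule the documents do not state. If confirmation is only a check and the Screening eye is kept whatever Day 1 shows, there is no bias. The schedule leans that way: eligibility review and prednisolone dispensing are both placed at Screening, so an eye has been named by then. Only part of the protocol was available here, and a reversal rule may sit in the rest. This stands, and it makes the point conditional. It does not remove it, because the SAP definition as written makes the Day 1 ranking part of what a study eye is.

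The size is also limited. Efficacy is descriptive, cohorts are small, no BCVA decision threshold appears in the supplied text, and errors shared within a visit roughly halve the central figures. All of that stands. SAP 9.7.1.6.2 tabulates BCVA change for both eyes, and the fellow eye would show a mirror-image fall. That offers a partial check but no correction.

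A reader might infer two stronger things. One is that the plan certainly builds in a gain of more than 2 letters. At a reading SD of 4 that figure needs eyes of nearly equal true acuity, independent errors and a reversal that changes who or what is analysed. The other is that the prednisolone pre-treatment adds to the gain. The documents do not say whether it changes Day 1 acuity or in which direction, so it supports only the point about order.

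**Conclusion.** The point holds in conditional form. If a failed Day 1 confirmation excludes the patient or switches the eye, the primary change and the responder proportions are biased upward in patients with two qualifying eyes. The central estimate is about 0.9 letters (exclusion) or 1.3 (switching), falling to roughly 0.5-0.7 with correlated errors. These sizes rest on an assumed reading SD and an assumed spread of between-eye differences.

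The worse-eye rule is read here as a ranking between qualifying eyes, so patients with one qualifying eye are unaffected. The cohort effect is diluted by a share the documents do not give. It lies well inside the sampling error of a single cohort and could not by itself explain a large gain. It is one-directional, however, so pooling cohorts would reduce the noise and not the bias. No type I error is at issue.

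Independently of size, the study-eye definition and the prednisolone footnote are out of order, and the supplied text leaves the efficacy eye undefined after a reversal. With ρ = 0 and τ = 8, about 27% of two-eye patients would reverse.

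**What to change.** Reconcile SAP 9.7.1.1.2 with footnote l in Protocol 1.3 and SAP Appendix I, so that the reading that ranks the eyes is not also the efficacy baseline. On statistical grounds, ranking on Screening BCVA and keeping Day 1 as an independent baseline removes the bias. Using Screening as the baseline as well would not, since that reading would then carry the selection. State what a Day 1 reversal means for the analysis, or cite the protocol section that already does. Which eye is treated after a reversal is for the sponsor and investigators to settle.

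For patients already dosed, analyse the eye on the dosing record and flag those with two qualifying eyes. Show the Week 4 BCVA change with and without them, by cohort and pooled across cohorts because single cohorts are small.

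The cost is a sentence or two in the documents and one more table row, with few patients per cell. Under Screening-only ranking, the study eye will occasionally read slightly better than its fellow on Day 1.

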9.7.1.2. Analysis of Patient Disposition

The number of patients enrolled at each site will be summarized by treatment cohort and overall using the FAS.

Patients' enrollment and disposition during the study will be summarized by treatment cohort and overall using the FAS. The reasons for discontinuation will be displayed in the order as they appear on the eCRF, and percentages will be calculated based on the number of patients who discontinued the study.

Summary tables will include the following. The percentages will be calculated based on the number of patients in the FAS.

- Number of patients screened
- Number and percentage of patients treated
- Number and percentage of patients treated who completed the study
- Number and percentage of patients treated who discontinued from the study
- The reasons for study discontinuation
- Number and percentage of patients attending each scheduled study visit

A listing of patients who do not meet all inclusion criteria or meet exclusion criteria will be provided. A table of major protocol deviations will be presented using the FAS.

9.7.1.3. Analysis of Demographic and Baseline Characteristics

9.7.1.3.1. Demographics and Disease Characteristics

Demographic and disease characteristics including age (years), age group (<65 years, \geq 65 years), sex, race, ethnicity, study eye (OD/OS), eye color, duration of DME, duration of diabetes, type of diabetes (type 1 or type 2), DME in the non-study eye, and prior laser photocoagulation in the study eye, will be summarized descriptively by treatment group and overall using the FAS. For categorical parameters, the percentages will be calculated overall and based on the number of patients in each treatment group based on non-missing observations.

Duration of diabetes and DME will be determined from the medical history page compared to date of consent. Presence of DME in the non-study eye, laser photocoagulation, and type of diabetes will be determined from medical history page.

9.7.1.3.2. Medical and Surgical History

Medical history will be coded using the Medical Dictionary for Regulatory Activities (MedDRA Version 25.0, Mozzicato, 2009). The frequency and percentage of patients with any medical history will be summarized by treatment group using the FAS. System organ class (SOC) will be sorted alphabetically and preferred term (PT) within each SOC will be sorted by overall descending order of frequency according to the following rules in order:

1. Descending frequency within AG-73305, 0.5 mg;
2. Descending frequency within AG-73305, 1 mg;
3. Descending frequency within AG-73305, 2 mg;
4. Descending frequency within AG-73305, 4 mg;
5. PT in alphabetical order.

The medical history will include both the ocular and the general (non-ocular) history. Ocular medical history and general (non-ocular) medical history will be summarized separately. Ocular and non-ocular medical histories are identified according to which CRF the event is recorded. Ocular medical history will be summarized separately for study eye and non-study eye.

9.7.1.3.3. Prior and Concomitant Medications

Prior and concomitant medications will be coded using the World Health Organization Drug Dictionary (WHODrug) (Version 2022-03, Lagerlund et al., 2020) for anatomical therapeutic chemical (ATC) classification and preferred drug name.

The frequency and percentage of patients with coded medications will be summarized by treatment group using the FAS. A patient who used multiple medications will be counted only once for each ATC and preferred drug name. Therapeutic Subgroup is sorted alphabetically, and preferred term is sorted by descending frequency overall within each Level 3 term according to:

1. Descending frequency within AG-73305, 0.5 mg;
2. Descending frequency within AG-73305, 1 mg;
3. Descending frequency within AG-73305, 2 mg;
4. Descending frequency within AG-73305, 4 mg;
5. PT in alphabetical order.

Prior and concomitant medications will be summarized separately. Ocular medications are defined as those medications for which an eye has been specified (OD, OS, or OU). Ocular and non-ocular medications will be summarized separately. Ocular medications will be summarized separately for study eye, non-study eye, and either eye.

Prior medications are defined as any medications that started and stopped prior to the first dose of study drug. Concomitant medications are defined as any medications that (1) start prior to the first dose of study drug and stop or are ongoing at or after the date of first dose of study drug; or (2) start at or after the first dose of study drug. Medications taken after Visit 9 or withdrawal from the study are not considered concomitant.

9.7.1.4. Analysis of Study Medication Compliance and Exposure

Not applicable as this is a single dose study.

9.7.1.5. Analysis of Efficacy

Summary descriptive statistics will be presented for all study visits at which efficacy data are collected. Efficacy analyses will be presented by cohort for the study eye using the FAS population. Data for efficacy assessments for the non-study eye will be provided in listings.

All efficacy data will be censored (set to missing) on or after the earliest instance of rescue therapy when summarized in tables. All data will be presented in listings.

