#### **Response Measures:**

##### *Safety assessments:*

- Adverse Events (AEs)
- ETDRS BCVA
- Intraocular pressure (IOP)
- Slit lamp biomicroscopy
- Dilated fundus exam (DFE)
- Crystalline lens assessment using AREDS scale
- Post-injection assessment
- Laboratory evaluation (hematology, serum chemistry and urinalysis)
- Electrocardiogram (ECG)
- Vital signs
- Physical examination
- Pregnancy test

*Efficacy assessments:*

- Improvements in ETDRS BCVA
- SD-OCT (Heidelberg Spectralis, dense scan) as measured by Central Reading Center (CRC)
  - Central subfield thickness (CST)
  - Ellipsoid zone (EZ)
  - External limiting membrane (ELM)
  - Intraretinal and subretinal fluid
  - Posterior vitreous detachment
- OCT-A as measured by CRC
  - Foveal avascular zone (FAZ)
  - Foveal capillary density (CD) (superficial and deep capillary plexuses)
- Diabetic retinopathy severity score (DRSS) assessed via color fundus photography
- Time to rescue medication

*Pharmacokinetics:* Plasma concentrations of AG-73305.

*Immunogenicity:* Serum levels of anti-AG-73305 antibodies (using binding and neutralizing antibody assays, if available).

**Study Population:** Approximately 25, adult male or female patients with center involving DME in the study eye will participate in the study, including a sentinel patient in each of 4 dose cohorts (see [Figure 1](#)).

**Phase:** 2a

**Description of Sites:** Approximately 8 sites in the United States will enroll patients.

**Description of Study Treatment:** AG-73305 is a humanized IgG1 Fc-fusion protein that targets vascular endothelial growth factors, placental growth factors and integrins. AG-73305 is a clear solution formulated in a 40 mg/mL concentration for intravitreal injection. Ascending doses of a single injection of AG-73305 will be assigned by cohort to 0.5, 1, 2, and 4 mg or until the maximally tolerated (or maximum administered) dose has been reached (see [Table 1](#)).

**Rescue Medication** will be standard-of-care anti-vascular endothelial growth factor (VEGF) administered by IVT in the study eye. Rescue medication is allowed at the Week 4 visit or later in patients meeting any of the following criteria:

- Loss of > 10 ETDRS letters from a previous best study visit with worsening of intraretinal or subretinal fluid observed by SD-OCT and judged by the Investigator to be the cause of the BCVA loss.

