9.7.1.5.2. Secondary Efficacy Analyses

Observed and change from baseline in CST as measured by SD-OCT at Week 1, 4, 8, 12, 16, 20 and 24 will be presented. A change from baseline in CST will indicate a positive response if the treatment difference is < 0 . Observed and change in intraretinal and subretinal fluid volumes, ELM and EZ by SD-OCT at each visit will also be presented. The presence of posterior vitreous detachment will be summarized by frequency and percentage.

Observed and change from baseline in FAZ and CD of the superficial and the deep capillary plexuses will be presented, as measured by OCT-A at the Baseline Visit, Week 4, and Week 24.

Observed and change from baseline in DRSS will be presented, assessed via color fundus photography at the Baseline Visit, Week 4, and Week 24.

Time from Day 1/Baseline to receipt of rescue medication in the study eye will be analyzed using Kaplan-Meier time-to-event analyses. Follow-up is measured to the earliest instance of receipt of rescue therapy in the study eye for patients receiving rescue therapy. Otherwise, patients are censored at the date they complete or discontinue the study. In addition, reasons for rescue and use of rescue medication by visit will be summarized by frequency and percentage. Rescue will be included at Visit X if the date rescue is provided is on or after Visit X and before Visit X + 1.

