2. ETDRS BCVA
3. Intraocular pressure (IOP)
4. Slit lamp biomicroscopy, including crystalline lens assessment using AREDS scale
5. Dilated fundus exam (DFE)
6. Post-injection assessment
7. Laboratory evaluation (hematology, serum chemistry and urinalysis)
8. Electrocardiogram (ECG)
9. Vital signs
10. Pregnancy test

The FAS will be used for all safety analyses. All data will be summarized as observed and no data imputation will be performed. No statistical treatment group comparisons will be performed, unless otherwise specified. Analyses will be presented by cohort and by study eye and non-study eye, if applicable.

Results from the physical examination performed at Screening will be presented in a listing.

All safety data will be censored (set to missing) on or after the earliest instance of rescue therapy when summarized in tables. All data will be presented in listings. This will impact the definition of TEAE.

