9.7.1.6.1. Adverse Events

AEs are coded using MedDRA Version 25.0. Treatment-emergent adverse events (TEAE) are defined as events that start on or after the administration of study medication and up to the earliest instance of rescue therapy. Pretreatment adverse events are events that begin prior to administration of study medication. Ocular AEs are defined as those events for which an eye has been specified (OD, OS, or OU).

Ocular and non-ocular treatment-emergent AEs will be summarized separately. Ocular AEs will be presented by study eye and non-study eye and overall (OU) if an event occurs in either eye.

In all summaries of AEs, percentages are calculated based on the number of patients in each treatment group of the Safety Analysis Set.

Overall summaries of AEs by treatment will include:

- the number of AEs and SAEs reported;
- the number and percentage of patients who experienced any AE;

- the number and percentage of patients who experienced any serious adverse event (SAE) and the reason for seriousness;
- the number and percentage of patients with any AE by worst severity and worst relationship.

The overall summaries of TEAEs will also include the number and percentage of patients with any TEAEs leading to study termination.

Summaries of the frequency and percentage of patients with AEs by SOC and preferred term by treatment group will include:

- All AEs by SOC and preferred term;
- All AEs by SOC, preferred term, and maximum severity;
- All AEs by SOC, preferred term, and maximum relationship.

System organ class (SOC) will be sorted alphabetically, and preferred term (PT) within each SOC will be sorted by overall descending order of frequency according to the following rules in order:

1. Descending frequency within AG-73305, 0.5 mg;
2. Descending frequency within AG-73305, 1 mg;
3. Descending frequency within AG-73305, 2 mg;
4. Descending frequency within AG-73305, 4 mg;
5. PT in alphabetical order.

Patients are counted only once for each SOC and PT. In summaries of maximum severity and maximum relationship, patients with multiple occurrences of events will only be counted once at the maximum severity/relationship per SOC and PT.

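### The SAP's rescue rule makes no exception for same-day values taken before the rescue injection; applied by calendar date, it removes a valid Week 4 primary BCVA value from the tables

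*SAP*

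**What the plan says.** **The rule.** For efficacy, SAP 9.7.1.5 says: "All efficacy data will be censored (set to missing) on or after the earliest instance of rescue therapy when summarized in tables". For safety, SAP 9.7.1.6 says: "All safety data will be censored (set to missing) on or after the earliest instance of rescue therapy when summarized in tables". SAP 9.7.1.6.1 defines TEAEs as "events that start on or after the administration of study medication and up to the earliest instance of rescue therapy". None of the three sections mentions assessments made on the rescue day before the injection, or says whether the boundary is a date or a time.

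**When rescue can happen.** The protocol synopsis says: "Rescue medication is allowed at the Week 4 visit or later in patients meeting any of the following criteria". The key efficacy endpoint in SAP 9.5.3 and 9.7.1.5.1 is the Week 4 minus Day 1 change in study-eye BCVA.

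**How the SAP handles timing elsewhere.** For study drug, SAP 9.7.1 splits the day at dosing: "Baseline values will be defined as the last measurement prior to dosing of study medication". For the table of rescue use by visit, SAP 9.7.1.5.2 works by date: "Rescue will be included at Visit X if the date rescue is provided is on or after Visit X".

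**OCT-A.** Footnote j of the schedule of activities requires OCT-A before the rescue treatment. SAP 9.7.1.5.2 says "Observed and change from baseline in FAZ and CD of the superficial and the deep capillary plexuses will be presented", for Baseline, Week 4 and Week 24.

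**Missing data.** SAP 9.7.1 says: "All analyses will utilize observed data only". A value set to missing is therefore not replaced, although it stays in the listings.

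**The concern.** The first permitted rescue visit and the primary endpoint visit are the same visit. A patient whose vision has fallen may be measured at Week 4, found to meet a rescue criterion, and injected that day. That day's BCVA was taken before rescue and is a clean reading of the AG-73305 effect, so there is no analytic reason to discard it.

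The rule as written invites a programmer to compare the assessment date with the rescue date and to blank everything where they are equal. The patient would then leave the Week 4 BCVA and CST summaries and the Week 4 OCT-A summary. Under the parallel safety rule, that visit's vision loss could also drop out of the table in SAP 9.7.1.6.2 of patients losing at least 5, 10 or 15 letters. With 3 to 8 patients per cohort (SAP 9.7.2), one patient carries 12.5% to 33.3% of a cohort's primary data.

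**Working it through.** **1. Can rescue fall on the Week 4 visit date?** Yes. The criterion of more than 10 letters lost with worsening fluid can be met at a single visit. So can the proliferative retinopathy criterion. The two-consecutive-visit criteria can be completed at Week 4, for example with Week 1 as the earlier visit.

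**2. Is the Week 4 value taken before rescue?** For OCT-A the order is explicit (footnote j). For BCVA and SD-OCT it is inferred: a criterion based on that day's BCVA or CST cannot be met until the value has been obtained.

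**3. What is lost under each reading?**

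| Rescue given | Boundary = date | Boundary = moment of injection |
|---|---|---|
| On the Week 4 visit date | Week 4 BCVA, CST and OCT-A lost from tables | Pre-injection values kept |
| On a later scheduled visit date | That visit's BCVA and CST lost (also OCT-A at Week 24) | Pre-injection values kept |
| Between visits or at an unscheduled visit | The preceding scheduled visit's values kept | The same |

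**4. Size when one patient is rescued on the Week 4 date.** The documents give no rescue rate, expected BCVA change or SD, so every value in this step is assumed. Let the other patients all be at +6 letters. The reported mean is then +6.0 whatever the rescued patient's value.

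Overstatement = (6 - rescued patient's change) / n

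| Rescued patient's change | n = 3 | n = 6 | n = 8 | Mean with value kept, n = 6 |
|---|---|---|---|---|
| -6 | 12/3 = +4.0 | 12/6 = +2.0 | 12/8 = +1.5 | (30 - 6)/6 = 4.0 |
| 0 | 6/3 = +2.0 | 6/6 = +1.0 | 6/8 = +0.75 | 30/6 = 5.0 |
| +6 | 0 | 0 | 0 | 36/6 = 6.0 |
| +9 | -3/3 = -1.0 | -3/6 = -0.5 | -3/8 = -0.375 | 39/6 = 6.5 |

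A cohort of 6 is close to the average, 25/4 = 6.25.

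**5. Why the sign can change.** Rescue counts loss from the best prior visit, so change from baseline = best change - loss.

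- More than 10 letters lost means at least 11. The change is below +6 whenever the best was below +17.
- More than 5 letters lost means at least 6. The change is below +6 whenever the best was below +12.
- The +9 row is a best of +20 with a loss of 11.

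Below these limits the mean is overstated; at or above them the effect can be zero or reversed.

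**6. Categorical summaries, -6 case, n = 6.** A gain of at least 5 letters goes from 5/6 = 83.3% to 5/5 = 100% if the denominator is observed patients, and stays 5/6 if it is the FAS. A Week 4 loss of at least 5 letters goes from 1/6 = 16.7% to 0/5 or 0/6.

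**7. How often a cohort would be affected.** The chance of at least one such patient is 1 - (1 - p)^n, the formula behind SAP Table 2. It reproduces that table to rounding: p = 0.05 gives 0.143, 0.265 and 0.337 for n = 3, 6 and 8, as printed. With assumed same-day Week 4 rescue rates of 2%, 5% and 10%, a cohort of 6 has at least one such patient with probability 0.114, 0.265 and 0.469.

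**The case against.** The strongest reply is that the rule speaks of an instance of rescue, not a date, and that the SAP writes *date* where it means one. SAP 9.7.1.6.1 ties similar boundary wording to the administration of study drug and places pretreatment events before it. The baseline definition also splits Day 1 at dosing. By analogy, a BCVA taken before the rescue injection precedes the instance and is kept. The date-based sentence in 9.7.1.5.2 only assigns rescue to a visit interval; it does not govern censoring.

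This stands as a possible reading, and it rules out the stronger inference that the SAP definitely discards pre-rescue Week 4 data. It does not settle the matter. The text attaches the word *on* to rescue without a within-day rule, and two programmers could produce different primary tables from it.

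Three further limits stand:

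- The loss arises only when rescue is given on the date of a scheduled visit.
- The magnitudes are wholly assumed.
- The study is descriptive. N is shown, and reasons for rescue, rescue by visit, time to rescue and full listings are reported. These help a reader notice the gap, but they do not restore the value to the Week 4 mean.

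A reader might also infer that an adverse event starting on the rescue date is left unassigned. The documents do not support that: 9.7.1.6 read with 9.7.1.6.1 excludes events from rescue onward. Only an event with no recorded onset time is open. Counting it as treatment-emergent would risk attributing effects of the rescue injection to AG-73305, so no default is argued for here.

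**Conclusion.** The point holds conditionally. SAP 9.7.1.5 and 9.7.1.6 lack a same-day exception. If they are applied by date, a patient rescued on the Week 4 visit date loses valid pre-rescue values from the primary and related tables. The same happens at any later scheduled visit with same-day rescue.

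Where BCVA triggered the rescue, the removed value tends to be poor. The Week 4 mean would then tend to be flattered: by 2.0 letters in the illustrated cohort of 6 at -6, and by 1.5 to 4.0 letters across cohorts of 8 down to 3. For rescue on CST alone or on proliferative retinopathy the direction for BCVA is uncertain, and a high best prior visit can bring the effect to zero or reverse it. It would go too far to infer a known bias in favour of AG-73305, because the documents give neither a rescue rate nor the expected changes.

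No test, power or alpha is affected. The rule should still be corrected: it can give a wrong primary summary, and the correction is cheap. Confidence is moderate, because the eCRF and the detailed rescue section of the protocol (6.5.3) could not be checked.

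**What to change.** In SAP 9.7.1.5 and 9.7.1.6:

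- Set to missing only assessments made after the first rescue injection.
- Keep assessments done on the rescue date before the injection in that visit's summaries and in the vision-loss table of 9.7.1.6.2.
- Where the order is not recorded, take scheduled BCVA and imaging on the rescue date as pre-injection.

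In SAP 9.7.1.6.1, use the same injection-time boundary for TEAEs.

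The cost is wording in three SAP sections, plus a pre/post-injection flag on rescue-day records or, if the eCRF does not capture the order, the default rule alone. No new assessments are needed and no clinical rule changes. The summaries may look slightly less favourable.
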